5.15.8. Quantitative motor data analysis

Data will include summary variables from individual motor tasks, generally indicating either response times and number of correct items. In addition, we will use factor analyses (or other means of creating composite scores from multiple variables) and examine factor scores as dependent variables.

Ancillary questions and analysis plans specific to quantitative motor analysis:

- 1. What are the key demographic and clinical variables, and the practice effects, that must be taken into account to maximize the sensitivity of the quantified motor data, such as age, education level, IQ, sex, etc.?
- 2. For individual tests, how do practice effects need to be taken into account to maximize utility in the context of a clinical trial?
- 3. Longitudinal analyses will be by principles set out in 5.14 and 5.15.1. Potential confounding is addressed in 5.15.2. The use of controls to study practice effects is addressed above in 5.14.

5.15.9. Imaging data analysis

T1- and T2- weighted images

Measures will include: VBM (Ashburner & Friston, 2000); BSI-derived rates for whole brain and caudate, atrophy and ventricular expansion (Freeborough & Fox, 1997); volumes from automated segmentation of striatal structures (Magnotta et al. 2002);. Cross-comparisons between each of these image-analysis methods will be undertaken.

Diffusion weighted imaging and Neurite Orientation and Dispersion Diffusion Imaging (NODDI)

We plan to perform well established compound measures of white matter integrity (e.g. fractional anisotropy, mean diffusivity, axial and radial diffusion, etc.). In addition, we plan to employ probabilistic fibre tracking to

Revised: 2nd September 2013 75 Version 5.2

determine white matter connection in the brain. We will also investigate neurite orientation and dispersion using the novel NODDI image acquisition.

Resting state fMRI analyses

We plan to perform seed region analyses and well as principal component analyses.

Activation fMRI analyses

fMRI activation data will be processed by correlating the onset of a movement with the changes in blood oxygenation caused by it. In addition, we plan to perform analyses of functional and effective connectivity. The analysis of fMRI data is well established and uses SPM .

Amide CEST and MTR

Levels of soluble and aggregated mutant HTT will be assessed using CEST and MTR image acquisitions respectively.

Each imaging measure will be assessed individually by determining the sample sizes needed in order to detect (with sufficient power) disease-modifying effects of various magnitudes. This will allow imaging measures to be compared, both with each other and with the other clinical phenotypic parameters. Secondary analyses will look at the associations between imaging measures and other measures (clinical assessments, CAG length, CAG-age prognosis, cognitive profile, neuropsychiatric scores, motor assessment, functional measures, wet biomarker profiling etc.). Note that, in addition to the usual CAG-age prognosis, CAG length is of separate interest for imaging and other biological markers, as modification of the huntingtin protein's biological effect is a function of CAG length.

The additional aim of the fMRI data is to look into disease heterogeneity and compensatory mechanisms that are in place at the pre-symptomatic stage of the disease. Network analyses, using e.g. Dynamic Causal Modelling [Friston et al, 2003) should help to identify the underlying networks.

Finally (as with all measures) models will be fitted to see whether a combination of measures (either within a modality or across modalities) can reduce the sample sizes needed to detect a disease-modifying effect.

5.15.10. Transcranial magnetic stimulation data analysis

Measures of the core protocol will include: somatosensory evoked potentials (SEP), long-loop reflexes, resting and active motor thresholds (RMT and AMT), input/output (I/O) curves, short afferent inhibition (SAI; 2 inhibitory interstimulus intervals (ISI), 2 facilitatory ISIs). Optional components consist of 5Hz paired associative stimulation (PAS) and EEG recording with individual TMS pulses

The core protocol will result in the following metrics:

MEP: latency (1 value)

SEP: latencies (N20) (1 value), amplitude/area under the curve of N20/P45 (1 value)

Long-loop reflexes (LLR): latencies (1 value for LLRI and LLRII), area under curve LLRII (1 value)

Cortical Relay Time (LLRII = MEP lat + SEP N20 + CRT)

RMT, AMT: 1 value each (%stimulator output)

I/O curve: slope from MEP size at three different stimulation intensities (110, 130, 150%RMT)

SAI: one value (% unconditioned) for inhibitory ISIs, one value (% unconditioned) for facilitatory ISIs

Each TMS measure will be assessed individually. This will allow TMS measures to be compared with each other and with the other clinical phenotypic parameters. Secondary analyses will look at the associations between TMS measures and other measures (clinical assessments, CAG length, CAG-age prognosis, cognitive profile, neuropsychiatric scores, oculomotor measures, motor assessment, functional measures, wet biomarker profiling etc.).

5.15.11. Oculomotor data analysis

The oculomotor data will be preprocessed from the raw data by the [name] group to extract the following variables:

- 1. The median latency of correct antisaccades (ms)
- 2. Antisaccade Error Rate (%)
- 3. Peak saccade velocity (deg/s)
- 4. Saccade velocity function (the slope of velocity/amplitude for correct antisaccades)
- Saccade latency variability for pooled correct and incorrect antisaccades (quantified as the standard deviation of the mean latency, and as the slope of the saccadic latency "LATER plot" (Reddi & Carpenter, 2000)

These measures are all established standard variables in the oculomotor literature. Statistical analyses will be based on methods and principles generally outlined in 5.14 and 5.15.1 Post hoc approaches will follow guidelines discussed in 5.15.2.

5.16. Sample size considerations

While sample size estimates can be calculated from the literature for individual measures for desired power, significance and effect sizes, this exercise can only be performed reliably over the interval originally studied. Extrapolated sample size estimates for other observation intervals or longer follow-up periods may be notably more inaccurate. Moreover, one of our aims is to generate multivariate, multimodal data with high temporal resolution. Until the desired measures have been made simultaneously, calculations cannot be performed to determine the required sample size for reliably identifying the optimum multimodal battery of measures in premanifest and early HD, or calculating the cohort size required for such a battery to be able to detect the effect of a disease modifying intervention.

Sample size estimates for TRACK-HD visits 5, 6 and 7 are based on the number of eligible PM and control participants available at the time of the calculation, which is approximately 123 PM and 102 controls. For potential longitudinal follow-up we assume a 10% loss in each of the groups, yielding 110 CAG-expanded and 92 controls. However, additional participants will be recruited in each group as specified above.

As of visit 4, few convincing longitudinal differences between PM participants and controls have been detectable. For measures continued since the study's inception, the additional 12 to 36 months of follow-up gained by visits 5, 6 and 7 will provide substantially greater power to detect meaningful longitudinal separation of the disease path. The precise increase in power depends on extrapolation of several assumptions about how within-participant measures continue to correlate over time. The nature of this continuing correlation may vary, depending on the measure, and is difficult to predict on the basis of the currently available observations. However, within a realistic range of continuing assumptions, visit 5 follow-up should allow us equivalent power to detect changes that are between 75% and 89% the effect detectable after visit 4 of the study of the study. At

visit 6, when total follow-up is 60 months, we will be able to detect effects between 58% and 80% of those detectable at 36 months of follow-up.

Based on published cross-sectional TMS data in premanifest HD, this proposed sample size would yield >99% power to detect equivalent published standardized effect size differences, even with a type 1 error rate of 0.1%. Thus, with a considerable margin of error, TRACK-HD has adequate power to detect cross-sectional TMS effects of the magnitude previously reported; there are no known longitudinal TMS studies on which to base sample size calculations.

For fMRI, cross-sectional effect sizes reported in the literature are between 1.0 and 1.5 for fMRI in early HD subjects but again there is a lack of longitudinal data. For visit 7, even splitting the different fMRI tasks across the two scanner types and thereby reducing the sample by a half, we still retain 80% power to detect cross-sectional effect sizes of 0.525. This allows a substantial safety margin for cross-sectional power, including allowing for publication bias which might reduce the reporting of false negatives and possibly smaller true effects in a predominantly preHD sample. Therefore, based on the literature reviewed, after making a range of assumptions about measurement reliability and the time course for the evolution of HD effects, we have judged it plausible that the proposed sample size would yield adequate power to detect longitudinal changes over 36 months of observation in visits 5, 6 and 7.

The novel amide CEST and NODDI imaging techniques have never been applied in Huntington's disease to date. Although cross-sectional and longitudinal data from a previous small single site MTR study did not provide conclusive information regarding sensitivity to premanifest disease (van den Bogaard et al, 2012; van den Bogaard et al 2013), we are employing this technique in unique combination with amide CEST imaging. MTR is acquired simultaneously during amide CEST imaging, requiring no additional acquisition time. We anticipate that this combined sequence will provide complementary information on both aggregated and mutant huntingtin buildup. These novel imaging techniques are necessarily exploratory and consequently we do not have data to estimate appropriate sample sizes.

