3.1. Overall study design

The generic Track-HD assessment plan is summarised in *new participants only

	Visit 1 (baseline)	Visit 2 (12 months)	Visit 3 (24 months)	Visit 4 (36 months)	Visit 5 (48 months)	Visit 6 (60 months)	Visit 7 (72 months)
Participants	90	90	90	90	60	60	60
Controls	30	30	30	30	30	30	30
Premanifest HD	30	30	30	30	30	30	30
Early HD	30	30	30	30	-	-	-
Pseudonymise	✓			√ *	√ *		
Check criteria	✓			√ *	√ *		
Demographics	✓			√ *	√ *		
Biosamples	✓	✓	✓	✓	✓	✓	✓
Clinical/motor	✓	✓	✓	✓	✓	✓	✓
Neuropsychiatric	✓	✓	✓	✓	✓	✓	✓
Cognitive	✓	✓	✓	✓	✓	✓	✓
Quantitative motor	✓	✓	✓	✓	✓	~	√
MRI	✓	✓	✓	✓	✓	✓	✓
DNA/LB sample	✓			√ *	√ *	✓	✓
Oculomotor	✓	✓	✓	✓	✓	✓	
TMS					✓	✓	✓

* new participants only

Table 1 Overall assessment plan

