5.2. Rationale

Candidate therapeutics with potential disease-modifying effects in HD are currently being tested (Ross and Tabrizi, 2011). Selective reduction of mutant HTT expression is one approach already being explored in preclinical studies, and compounds suggested to promote clearance of mutant HTT are being studied in phase Ib and phase IIa trials. However, there have so far been no successful disease-modifying phase III clinical trials in HD; such trials ultimately rely on the development of objective and quantitative outcome measures, particularly when considering trials before overt symptom onset. Therefore, it is highly desirable to validate measures that allow efficacy-testing over relatively short intervals using practical sample sizes in a cohort which may best respond to therapeutic interventions, namely those in the earliest stages of the disease.

Track-HD is an international, multi-centre study which is designed to determine the individual and joint utility of a selected set of clinical and biological outcome measures. Track-HD integrates prospectively- and systematically-collected clinical research data (e.g. phenotypic clinical features, family history, demographic characteristics) with biological specimens. We will measure clinical and biological markers, including neuropsychiatric, cognitive, quantitative motor, oculomotor, imaging markers, and laboratory biomarkers.

Several imaging, cognitive, and motor measures have been proposed as suitable candidates for tracking disease progression, but so far most studies have relied on cross-sectional data to infer usefulness (for review see Weir et al 2011). Such inferences risk overestimating the sensitivity of measures because cross-sectional group differences might represent the accumulation of up to 25 years of neurodegeneration. Longitudinal studies over durations relevant to clinical-trial timelines are therefore essential, but few studies have described change within premanifest and early stage HD, particularly over short periods. In TRACK-HD we have previously reported significant progressive white-matter, regional, and whole-brain atrophy over 12 months across the spectrum of

disease from premanifest to early stage HD (Tabrizi et al 2011); we have also observed accompanying deterioration in clinical, motor and cognitive measures in early HD.

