5.5.10. Transcranial Magnectic Stimulation (TMS)

5.5.10.1. Overview

TMS is a non-invasive in-vivo motor cortex stimulation, which provides an insight into the electrophysiological properties of corticospinal neurons and the trans-synaptic regulation of inhibitory and facilitatory circuits within the motor cortex. It has previously been used to demonstrate abnormalities in motor cortex excitability in heterogeneous, manifest and premanifest populations (Schippling et al, 2009). These abnormalities include prolonged cortical silent periods, reduced short interval intra-cortical inhibition and enhanced or normal intra-cortical facilitation.

It is also well-known that somatosensory evoked potentials (SEPs) become abnormal as HD progresses. This might reflect a disease-related influence on the sensory input part of sensory-motor integration pathways. One such pathway that can be tested easily in humans is short latency afferent inhibition (SAI in which a transient sensory input leads to a rapid and short-lasting inhibition of the motor cortex). Since SAI is thought to reflect changes within the somatosensory-motor pathways in HD, it may also be worthwhile to consider comparisons with cognitive tasks that include aspects of motor integration.

The aim is to focus on the primary sensory-afferent inhibition (SAI) variable, and perform comparisons with a wider range of quantitative motor and imaging methods. The TRACK-HD premanifest cohort is sufficient to meet sample size estimates for the SAI and over 24 months would have the additional advantage of being able to compare not only those near and far from onset, but also potentially fast and slow progressors. The cohort also benefits from the existing 36 months of data to inform these new cross-sectional and longitudinal studies.

Test/Method	Duration (min)	Measurement / Analysis			
Core protocol	Core protocol				
Transcranial Magnetic Stimulation	15	Hot-spot determination and motor thresholds (rest and active)			
	8	Cortical silent periods and input-output curves at 110, 130 and 150% of RMT at rest, and 130, 150 and 175% of AMT with pre-activation.			
	7	Short latency afferent inhibition*			
Evoked potentials	3	Sensory evoked potentials			
	3	Long-latency reflexes			
Visual Evoked potentials (VEP) ¹	15	VEP P2 latency, N1/P2 and P2/N2 amplitude			
TMS Evoked potential (TMS-EEG) ²	20	Baseline EEG; EEG with TMS. Differences between baseline and TMS EEG			
Optional components					

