5.14.2. General principles of statistical analysis

We will strive to always distinguish between a priori and post hoc hypotheses, with a priori hypotheses defined as comprehensively as possible before data analysis begins. An honest distinction is critical to true progress and optimal allocation of future resources in HD research, since the nominal statistical significance for a post-hoc hypothesis, suggested only by preliminary exploration of the data, is typically inflated in ways that are often impossible to quantify (Good & Hardin, 2006).

We will rely on mixed effect linear models to assess most longitudinal change (Verbeke & Molenberghs, 2000; Littell et al., 2006). Fixed effects will typically include group (diagnosed, premanifest, or control), age, gender, time-since-first-measurement ("time", which will be 0 at baseline), and interactions between group and time. Substantial interactions between group and time will usually be the main parameters of interest. Other fixed covariates will be determined by anticipated confounders for the specific outcomes. For example, most psychometric tests require adjustment for years of education.

Depending on the year of enrolment and study visit at which an assessment was introduced for the first time, the number of existing measurements for each TRACK-HD assessment will range from 2 to 4 measurements over 1 to 3 years. Additional data collected for these assessments will contribute to the overall ongoing longitudinal analyses. For new assessments, e.g. fRMI, and TMS, and/or new participants there will be 3 measurements over 2 years; and Viritual Maze task, Go-No-Go task, VEPs, TMS-EEG, CEST, NODDI and MTR there will be cross-sectional data only.

Our primary hypotheses will treat time as a linear effect unless there is a compelling a priori reason to use varying degrees of freedom in estimating separate effects for specific participants and/or assessments. Secondary analyses will typically explore whether longitudinal change is related to estimated prognosis within the premanifest group (based on CAG and age). Random effects will always include a within-participant term. Our sample size will be such that we will generally model unstructured within-participant covariance over visits. Other candidate random effects will include variance components for study site and examiner, as appropriate.

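### Section 5.16 judges longitudinal power over 36 months of visits 5 to 7, but measures and participants that start at visit 5 have at most 24 months, and adequate power for them is not shown

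*Protocol*

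**What the plan says.** The sample size section (5.16) treats two kinds of measure separately. For measures continued since the study began, it counts 12 to 36 months of added follow-up from visit 4 and describes how much smaller the detectable effects become. For TMS and fMRI it gives cross-sectional power only. TMS has more than 99% power for published premanifest effect sizes at a 0.1% type 1 error. fMRI has 80% power for an effect size of 0.525 at visit 7, with the sample halved because each task is run on one scanner type. The published fMRI effect sizes it cites, 1.0 to 1.5, are from early HD. It says that no longitudinal TMS studies are known and that longitudinal fMRI data are lacking.

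The fMRI paragraph then concludes, as a consequence of what precedes it: "the proposed sample size would yield adequate power to detect longitudinal changes over 36 months of observation in visits 5, 6 and 7". The conclusion is worded as a judgement, reached "after making a range of assumptions about measurement reliability and the time course for the evolution of HD effects, we have judged it plausible". No longitudinal effect size, standard deviation, correlation or power value accompanies this.

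Other sections give the actual time frame. Tables 1 and 10 place visits 5, 6 and 7 at 48, 60 and 72 months. Section 5.14.2 states: "For new assessments, e.g. fRMI, and TMS, and/or new participants there will be 3 measurements over 2 years". Section 5.5.10.1, on SAI, says that the cohort "over 24 months would have the additional advantage of being able to compare not only those near and far from onset".

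**The concern.** The paragraph concerns modalities with no visit 4 value. fMRI and TMS entered with the visit 5 to 7 extension, so their first-to-last span cannot be 36 months. The same limit applies on every measure to the participants recruited at visit 5 (33 controls and 30 premanifest, section 5.6.4).

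The reasoning also takes a step that the protocol itself cautions against. Section 5.2 says that inferring usefulness from cross-sectional data risks overstating sensitivity, because "cross-sectional group differences might represent the accumulation of up to 25 years of neurodegeneration". Section 5.16 opens by warning that estimates extrapolated to other observation intervals may be notably less accurate.

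Longitudinal change is the primary object of study (section 5.14.1). A reader planning a later trial, or interpreting a flat fMRI or TMS trajectory, needs to know whether the study was sized to see change over the interval actually observed.

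**Working it through.** **1. The protocol's one quantified fMRI figure.** It states 80% power at d = 0.525 with half the sample. I used power = Φ(d / √(1/n₁ + 1/n₂) − 1.96). Two-sided 5% is my assumption, since no alpha is stated for this figure.

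- Available sample 123/102, halved to 61.5/51: √(1/61.5 + 1/51) = 0.189; 0.525/0.189 = 2.77; power 0.79.
- Target sample 120/120 (30 per group at four sites), halved to 60/60: √(2/60) = 0.183; 0.525/0.183 = 2.88; power 0.82.
- Sample after the protocol's 10% loss, 110/92, halved to 55/46: √(1/55 + 1/46) = 0.200; 0.525/0.200 = 2.63; power 0.75.

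The figure reproduces to within about 2 points at the available or target sample. It is cross-sectional and says nothing about change.

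**2. The observation window.**

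| What is followed | First to last | Span |
|---|---|---|
| Continued measures, counted from visit 4 | 36 to 72 months | 36 months |
| Measures first taken at visit 5 and kept to visit 7 | 48 to 72 months | 24 months, three visits |
| Participants enrolled at visit 5 | 48 to 72 months on the study clock | at most 24 months |
| SAI (5.5.10.4, Table 10) and the new antisaccade test (5.5.11.3, Table 10) | 48 to 60 months | 12 months, two visits |

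Only the first row gives 36 months, and section 5.16 deals with that group in an earlier paragraph.

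**3. What the longitudinal judgement rests on.** No longitudinal power can be computed, because the protocol supplies no longitudinal effect, standard deviation or within-participant correlation for fMRI or TMS. Only the relative effect of the shorter window can be illustrated.

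**4. Illustration of the window's effect.** Section 5.14.2 makes the group-by-linear-time interaction the main parameter, so slope precision is the relevant measure. Write the between-person slope variance as x times the residual variance, with time in years. The variance of one participant's estimated slope is then proportional to x + 1/SS, where SS is the sum of squared time deviations.

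- Three annual visits (0, 1, 2): SS = 2. Four annual visits (0, 1, 2, 3): SS = 5.
- Ratio of standard errors = √((x + 1/2)/(x + 1/5)).
- x = 0: √(0.5/0.2) = 1.58. x = 0.25: √(0.75/0.45) = 1.29. x = 1: √(1.5/1.2) = 1.12.
- Under random-walk correlation, where precision depends on total duration: √(3/2) = 1.22.
- If the 36-month comparator is three visits at 0, 18 and 36 months, SS = 4.5 and the x = 0 ratio is √(4.5/2) = 1.50.

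At equal sample size, the smallest detectable annual rate grows by the same factor, about 1.1 to 1.6 over these structures. All the covariance structures are my assumptions.

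**The case against.** The strongest defence is that the sentence is a declared plausibility judgement, not a calculation. It refers to assumptions about reliability and time course, which are what one would use to move from cross-sectional to longitudinal effects. The protocol openly admits the lack of longitudinal data, section 5.14.2 has the correct two-year span, and no analysis depends on the 36-month phrase. Thirty-six months is also the nominal length of the extension, so loose wording is a likely explanation. All of this stands, and it limits the point to the stated window and the missing assumptions. It does not rescue the sentence, which names visits 5, 6 and 7 and gives them a span that they do not have. Section 4.3, moreover, says without any hedge that sample size calculations support the extension.

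A reader might infer more: that the extension is underpowered for fMRI and TMS, or that a nominal 80% power falls to some specific lower value. The documents do not support this. The protocol plans no longitudinal effect at 80% power, and the ratio in step 4 tends to 1 as between-person slope variance grows. Scaling the early-HD effects down by assuming linear accrual over decades would be a further construction. Section 5.2 points away from linearity, reporting functional decline at 36 months only in people under 10 years from predicted onset.

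A reader might also apply the halved sample throughout. Section 5.16 ties it to task fMRI at visit 7. Resting fMRI is scheduled at all sites, and the halving does not concern TMS.

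Finally, that a null trajectory would be reported as an adequately powered negative is conjecture. Section 5.15.1 plans estimates with standard errors, and sample sizes for future trials with confidence intervals.

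**Conclusion.** The 36-month window in section 5.16 is wrong as written for the measures that its paragraph covers. They have at most 24 months and three visits, and SAI has 12 months and two visits. The new antisaccade test, outside that paragraph, also has 12 months. Participants enrolled at visit 5 have at most 24 months on any measure. The span follows directly from the visit schedule and needs no assumption.

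Adequate longitudinal power for these measures is not shown, because only cross-sectional effects are reported (the fMRI ones from early HD) and the bridging assumptions are not given. It is not proven absent. The factor of about 1.1 to 1.6 on the slope standard error only illustrates what the shorter window can cost and depends on the assumed covariance. Continued measures followed from visit 4 are unaffected.

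**What to change.** In section 5.16:

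- Replace 36 months with at most 24 months (three annual visits) for measures introduced at visit 5 and kept to visit 7, and for participants enrolled at visit 5.
- State 12 months (two visits) for SAI and the new antisaccade test.
- Keep 36 months only for measures and participants continuing from visit 4.
- Withdraw the inference from cross-sectional effects to longitudinal power.
- Then do one of two things. Either state the minimum detectable premanifest-control slope difference over the actual window, under a stated range of within-participant correlation, using the reduced visit 7 sample for each task-fMRI paradigm only. Or label these longitudinal analyses exploratory, as the section already does for CEST and NODDI.

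The cost is a few sentences, a short calculation and a less favourable power statement. No extra participants or visits are needed.
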